5.3 Study Endpoints and Statistical Plan

All endpoints will be determined according to an intention to treat analysis. The primary thrombotic endpoint will be platelet responsiveness (PRU) using the VerifyNow assay at 1 day post procedure. Platelet reactivity in the Clopidogrel and Ticagrelor groups will be compared

TABLE 1. Inclusion/Exclusion Criteria

Inclusion criteria:

- 1) Valvular heart disease and a clinical indication for TAVR,
- 2) Age of 18 years or older,
- 3) Capable of informed consent.
- 4) Planned transfemoral TAVR.

Exclusion criteria:

- 1) Prior history of stroke, transient ischemic attack (TIA), or intracranial hemorrhage,
- 2) Established bleeding diathesis or thrombocytopenia (<150k/dl),
- 3) End-stage renal disease,
- 4) Severe hepatic impairment or liver cirrhosis,
- 5) Pregnancy,
- 6) Current infection,
- 7) History of autoimmune disease,
- 8) Established allergy to contrast agents, thienopyridines, aspirin, or ticagrelor,
- 9) History of solid organ transplantation,
- 10) Atrial Fibrillation, DVT, PE or other indication for long term anti-coagulation,
- 11) Plan for direct aortic access or trans-apical TAVR,
- 12) Enrollment in another clinical trial,
- 13) Recent (< 12 months) or active excessive bleeding.

using an independent samples t-test (or non-parametric test as appropriate), with significance declared for p-values <0.025 . The primary inflammatory endpoint is the percentage of inflammatory monocytes (compared to total monocytes) as a continuous variable 1 day after TAVR. The percentage of inflammatory monocytes in the Clopidogrel and Ticagrelor groups will be compared using an independent samples t-test (or non-parametric test as appropriate), with significance declared for p-values <0.025 . The percentage of inflammatory monocytes will also be compared over multiple time points to determine the trajectory and duration of the immune response, to guide duration of treatment in future studies. The values at baseline, 1 day, and 7 day will be compared within group using exploratory longitudinal mixed models to determine the kinetics of convalescence and between groups to establish whether treatment effects exist. Models that include the 30-day values also will be fit. Time period will be considered both as a continuous covariate (in days), as well as a categorical variable. Inferential interest will focus on treatment by time interaction. These models will also be used to explore the relationship between the level of P2Y12 inhibition and the reduction in inflammatory monocytes between treatments. This relationship could be different given that Ticagrelor is not only a more potent P2Y12 antagonist as compared with clopidogrel but may also have a unique dual mode of action; P2Y12 antagonism complemented with adenosine uptake inhibition.

Secondary measures of thrombotic and immune status will be crucial for the determination of mechanism and to guide future studies. These will include: platelet-leukocyte aggregates, platelet P-selectin and activated GPIIb/IIIa expression, markers of T-cell activation (i.e., HLA-DR/CD38 co-expression), and plasma markers of inflammation (CRP, IL-6, TNF- α , IL-6, sCD14, CD40L, oxidized LDL) and thrombosis (thrombin-antithrombin complexes, F1.2, soluble P-selectin, S100A8/A9, D-dimers). These secondary measures will be analyzed as continuous variables at baseline, 1 day, 7 days, and 30 days. PBMC will be isolated and will be used to assess T cell activation as continuous variables using the percentage of HLA-DR+/CD38+ CD4 and CD8 T-cells. These values at the specified time points will also be compared within group using longitudinal mixed models to determine their kinetics and between groups to establish whether a treatment by time interactions exists.

[figure not shown]

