Patients will receive a baseline blood draw prior to TAVR. Patients will then have blood draws at 24 hours, 7 days, and 30 days post procedure. Patients will be seen in followup according routine clinical practice at 7 and 30 days. All blood samples will be obtained using a 30 mL syringe which is then transferred into tubes containing 3.2% sodium citrate (blue top) or K2-EDTA (purple top). Aliquots of whole blood will be used for platelet responsiveness studies, monocyte flow cytometry, leukocyte-platelet interaction, and T cell activation studies. Plasma and Peripheral blood mononuclear cells (PBMC) will be cryopreserved at -80 and -150 degrees, respectively. Plasma based assays will be batched and performed at intervals using freshly thawed cryopreserved samples.

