5.6 Power Calculation and Sample Size Estimate

Our power calculation is based upon the inflammatory co-primary endpoint, using our preliminary data. In preliminary studies of 25 patients undergoing TAVR, the mean proportion of inflammatory monocytes 1 days after TAVR was 20.0% with a standard deviation of 5.0 %. Thus, a total of 60 patients, randomized 30:30 would be expected to have 80% power to detect an absolute effect of 4% (i.e. ticagrelor treated patients having 16 % percent inflammatory monocytes), using a two sided t-test with Type I error of 0.025. Note that we are using Bonferroni correction, to account for two primary outcomes. We expect dropout of randomized patients to be less than 10% prior to the 1 day blood draw. All randomized patients will be analyzed using an intention to treat analysis. We will assess the missing completely at random assumption by comparing results with analyses derived by assuming that the data is missing at random (MAR), and use of multiple imputation approaches.

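### The day-1 t-tests for both co-primaries are valid but leave the planned baseline sample unused; pre-specified baseline adjustment would be a near-free gain if baseline predicts day 1

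*Combined protocol and SAP*

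**What the plan says.** Section 5.3 defines two co-primary endpoints, each measured 1 day after TAVR and each tested at 0.025. For PRU, "Platelet reactivity in the Clopidogrel and Ticagrelor groups will be compared" by an independent-samples t-test or a non-parametric test. For monocytes, "The percentage of inflammatory monocytes in the Clopidogrel and Ticagrelor groups will be compared using an independent samples t-test", with the same fallback. Neither test includes a baseline value.

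Section 5.6 sizes the trial on the monocyte endpoint, "using a two sided t-test with Type I error of 0.025", so the planned test and the sample-size calculation agree.

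Section 5.2 provides the baseline data: "Patients will receive a baseline blood draw prior to TAVR". Its assay list is not restricted to post-procedure samples: "Aliquots of whole blood will be used for platelet responsiveness studies, monocyte flow cytometry". Baseline monocyte percentage is named as an analysis variable in 5.3. Baseline PRU is not, and is only inferred from the draw and the assay list.

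For the co-primary measures, 5.3 uses baseline in one place: "The values at baseline, 1 day, and 7 day will be compared within group using exploratory longitudinal mixed models". For those models, "Inferential interest will focus on treatment by time interaction". They are labelled exploratory and do not decide either co-primary.

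**The concern.** In a 60-patient trial, a pre-treatment measurement of the outcome is often the cheapest source of precision. If the baseline value predicts the day-1 value, a t-test on day 1 alone leaves that explained variance in the error term. Nothing is biased and type I error is not at risk; what is at stake is power. Section 5.6 has little of it to spare, because the target is 80% with 60 patients and the number is not raised for the dropout it anticipates (under 10% before the day-1 draw).

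The exploratory mixed models do not fill this role. Besides not being the primary test, their efficiency at day 1 depends on a parametrisation that 5.3 does not give. If each arm has its own baseline mean, the day-1 treatment-by-time contrast is a comparison of change scores, which can be weaker than the plain t-test. If the arms share a baseline mean and the covariance is unstructured, the contrast equals the ANCOVA estimate on complete data.

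**Working it through.** **Inputs.** From 5.6: day-1 monocyte mean 20.0%, SD 5.0, difference 4 points (20% versus 16%), 30 per arm, two-sided alpha 0.025, dropout below 10%. Assumed, because the documents do not give them: the baseline to day-1 correlation r and, for change scores only, the baseline SD s.

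**1. The plan's own figure.** Noncentrality = 4 / (5 × √(2/30)) = 3.098.
- Normal approximation: Φ(3.098 − 2.241) = 80.4%, so the stated 80% reproduces.
- Noncentral t with 58 df: 78.5%.
- With 27 per arm (a full 10% loss): 73.5%.

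**2. ANCOVA on baseline.** With k covariates and n per arm, residual variance = 25 × (1 − r²) × [1 + k/(2n − k − 3)], df = 2n − 2 − k. The bracket is the cost of estimating the slope. For k=1 and n=30 it is 1 + 1/56. At r=0.5 the variance is 25 × 0.75 × 1.0179 = 19.08, so SD = 4.369, noncentrality = 3.546, df = 57 and power = 89.0%.

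| r | 30 per arm | 27 per arm |
|---|---|---|
| unadjusted t-test | 78.5% | 73.5% |
| ANCOVA, 0 | 77.7% | 72.5% |
| ANCOVA, 0.2 | 79.5% | 74.4% |
| ANCOVA, 0.3 | 81.8% | 76.9% |
| ANCOVA, 0.5 | 89.0% | 85.0% |

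At 30 per arm, ANCOVA breaks even at r=0.14 and reaches 80% at r=0.23. At 27 per arm it reaches 80% at r=0.39. With two covariates at 30 per arm, power is 76.8% if neither predicts anything (a cost of 1.7 points), and break-even moves to r=0.19.

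**3. Change score, for comparison.** Variance = 25 + s² − 2 × r × 5 × s, df = 58, 30 per arm.

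| r | s = 5 | s = 2.5 |
|---|---|---|
| 0 | 46.1% | 68.1% |
| 0.3 | 62.6% | 80.7% |
| 0.5 | 78.5% | 89.6% |

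The change-score variance is never below that of ANCOVA before the slope cost. At s=5 the ratio is 2.00, 1.54 and 1.33 for r = 0, 0.3 and 0.5. At s=2.5 and r=0.5 it is 1.00 and the two coincide. Change from baseline is therefore not a safe substitute.

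**4. Type I error at 30:30** (simulation, normal data, 100,000 trials per cell, nominal 2.5%, r = 0, 0.3, 0.5).
- t-test: 2.47%, 2.54%, 2.48%.
- ANCOVA, model-based standard error: 2.43%, 2.57%, 2.47%.
- ANCOVA, HC3 standard error: 2.12%, 2.23%, 2.19%, at a cost of about 1.2 to 1.9 points of power.
- Rank ANCOVA: 2.47%, 2.64%, 2.55%.

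With arm SD ratios of 1.5 and 2.0 at r=0.5, model-based ANCOVA gives 2.56% and 2.60%, and rank ANCOVA 2.84% and 3.38%.

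**5. PRU.** Section 3 reports PRU only after TAVR and only on clopidogrel (median 244.5, interquartile range 164.8 to 290.3, n=28). There is no planned PRU difference, baseline distribution or correlation, so no gain can be computed.

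**The case against.** The planned analysis is legitimate: an unadjusted test of a randomised endpoint, matched to its own sample-size calculation. Adjustment is an efficiency preference, and its benefit rests on an r that nothing in the documents supports or excludes. That r could be low, since section 4 describes a marked monocyte expansion within 24 hours of the procedure. At r=0.2 the gain is 1.0 point, and below 0.14 it is a small loss. All of this stands, and it is why the point is only one to consider. It does not remove the asymmetry between a bounded loss and a potentially useful gain.

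For PRU, the benefit is unquantified and baseline PRU is only inferred. Patients may or may not already be on a P2Y12 inhibitor, so baseline values may mix on-drug and off-drug readings. This stands: the PRU part depends on a confirmed pre-dose baseline measurement.

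The statement that the model-based standard error is adequate applies to equal analysed arms. With 26 versus 30 patients and twice the SD in the smaller arm, ANCOVA's type I error is about 3.4%, but the planned pooled t-test gives 3.3%, so the weakness is not created by adjusting. Similarly, with an SD ratio of 2 at 30:30, the Wilcoxon test gives 3.1% against 3.4% for rank ANCOVA; most of that sensitivity already exists in the planned fallback.

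Finally, section 5.1 refers to Figure 2 for participant flow. The figure is not in the copy reviewed and may already fix the order of draw and first dose, so the timing cannot be counted as a gap in the plan.

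**Conclusion.** The point holds as an optional improvement, not an error. The t-tests are valid, alpha is correctly split and the stated 80% reproduces. For the monocyte endpoint at 30 per arm, baseline adjustment would change power by −0.8 points at r=0, +3.3 at r=0.3 (81.8 − 78.5) and +10.5 at r=0.5 (89.0 − 78.5). These figures assume normal data, the plan's SD and difference, a common slope in both arms, and a baseline taken before the first study dose. The last condition matters because 5.2 times the draw only relative to TAVR, while the Synopsis and 5.8 place the first dose before TAVR as well. A post-dose baseline could carry part of the treatment effect. The planned t-tests are unaffected by this; any analysis using baseline is not, including the exploratory models in 5.3.

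**What to change.** In 5.3, before any between-arm comparison is seen:

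- Pre-specify, for each co-primary, an ANCOVA of the day-1 value on treatment and the baseline value of the same measure, tested at 0.025.
- Name one rank-based or transformed version for non-normal data, with the rule for using it.
- Fix one standard-error method. The model-based one is adequate at 30:30.
- State one method for a missing baseline value, for example the mean of both arms pooled. Section 5.6 says "We will assess the missing completely at random assumption by comparing results" with multiple-imputation analyses, but does not say how a missing baseline covariate would be handled.
- Keep the unadjusted test as a sensitivity analysis.
- Optionally, add P2Y12-naïve status as a covariate for PRU.

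In 5.2, state that the baseline sample is drawn before the first study dose and that PRU is measured on it, or confirm that Figure 2 already says so.

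The cost is SAP wording, one timing sentence for a draw already planned, and one degree of freedom (about 0.8 points of power at 30 per arm if r=0). A second covariate brings the cost to about 1.7 points in the monocyte scenario if neither is predictive. No extra patient, visit or draw is needed; if PRU is not already run on the baseline sample, that assay would be added.

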Inflammation and Thrombosis in Patients With Severe Aortic Stenosis After
Transcatheter Aortic Valve Replacement (TAVR)

NCT02486367

January 31, 2019

Supplementary Clinical Study Protocol

Title: Platelet and Monocyte Activation After Transcatheter Aortic Valve Replacement (POTENT-TAVR)

Subtitle: POTENT-TAVR: A Mechanistic Randomized Trial of Ticagrelor versus Clopidogrel

Table of Contents

1. Cover page	2
2. Synopsis.....	3
3. Introductory Background.....	4
4. Study objectives.....	6
5. Study design.....	7
6. References.....	12

1. Cover page

Title: Platelet and Monocyte Activation After Transcatheter Aortic Valve Replacement (POTENT-TAVR): POTENT-TAVR: A Mechanistic Randomized Trial of Ticagrelor versus Clopidogrel

Acronym: POTENT_TAVR

Test drug: Ticagrelor

Active Control: Clopidogrel

Clinical study phase: Phase 4

Sponsor: AstraZeneca

Principal Investigator:

[name]

Associate Professor of Medicine

Case Western Reserve School of Medicine

[name]

[contact]

Compliance Statement:

The study will be conducted in compliance with the protocol and any applicable regulatory requirements.

Confidentiality

The information provided in this document is strictly confidential and is intended solely for the guidance of clinical investigation. Reproduction or disclosure of this document - whether in part or in full - to parties not associated with the clinical investigation, or its use for any other purpose, without the prior written consent is not permitted.

2. Synopsis

Title: Platelet and Monocyte Activation After Transcatheter Aortic Valve Replacement (POTENT-TAVR)

Clinical study phase: Phase 4

Study objective(s): 1. To determine whether high-potency ADP receptor blockade reduces measures of platelet activation in patients after TAVR. 2. To determine whether high-potency ADP receptor blockade mitigates the pro-thrombotic inflammatory response observed after TAVR.

Test drug: Ticagrelor

Dose: 90mg twice daily

Route of administration: Oral

Duration of treatment: The first dose of Ticagrelor will be started (180mg load) the morning of planned TAVR. Treatment will continue for 30 days.

Active Comparator: Clopidogrel

Dose: 75 mg once daily

Route of administration: Oral

Duration of treatment: The first dose of Clopidogrel will be given (300 mg load if P2Y12 naïve or 75mg if P2Y12 non-naïve) the morning of planned TAVR. Treatment will continue for 30 days.

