5.8 Treatment assignment

Randomization will be performed via seal envelop system. Opaque envelopes (60) will be filled with a sheet of paper in which Ticagrelor (30) or Clopidogrel (30) is written and envelopes are to be opened after informed consent is received and on or before the start of the TAVR such that study drug initiation occurs prior to TAVR. Randomization envelops are stored securely at the Clinical trials office at University Hospitals (UH).

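### In the categorical-time mixed models of 5.3, a treatment-by-time test with separate baseline means by arm can waste precision that a common-baseline constraint would keep, provided the baseline sample precedes the first study dose

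*Combined protocol and SAP*

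**What the plan says.** For inflammatory monocytes, section 5.3 states: "The values at baseline, 1 day, and 7 day will be compared within group using exploratory longitudinal mixed models". The same models serve the between-group comparison. It adds: "Models that include the 30-day values also will be fit". On the coding of time: "Time period will be considered both as a continuous covariate (in days), as well as a categorical variable". The target is then named: "Inferential interest will focus on treatment by time interaction".

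Later in 5.3 the secondary thrombotic and immune markers, measured at baseline and days 1, 7 and 30, get the same treatment, with comparison "between groups to establish whether a treatment by time interactions exists".

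The plan does not write out the model. It mentions no baseline constraint, baseline covariate or covariance structure.

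On timing, section 5.2 says: "Patients will receive a baseline blood draw prior to TAVR". The Synopsis says: "The first dose of Ticagrelor will be started (180mg load) the morning of planned TAVR". Section 5.8 has envelopes opened "such that study drug initiation occurs prior to TAVR". Both the baseline draw and the loading dose therefore come before the procedure, and the readable text does not say which comes first.

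The co-primary day-1 comparisons are separate unadjusted two-sample tests.

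**The concern.** When baseline is an outcome time and time is categorical, a model with treatment, time and their interaction gives each arm its own baseline mean. The interaction at a later visit is then the arm difference at that visit minus the arm difference at baseline. If the baseline sample is taken before dosing, randomisation makes the second term zero in expectation, and subtracting it in full contributes only sampling error.

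The mixed models carry the longitudinal between-arm results for monocytes and for the secondary markers, which 5.3 presents as important for mechanism and for planning later studies. With 30 patients per arm there is little precision to spare. If baseline and day 1 are weakly correlated relative to their SDs, the interaction contrast can be less precise than a plain day-1 comparison. A positive day-1 t-test could then stand beside a non-significant interaction on the same data, with nothing in the plan to explain the discrepancy.

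**Working it through.** **Inputs from the documents.** 30 per arm (5.1, 5.6); day-1 SD of 5.0 and a 4-point effect (5.6); two-sided type I error 0.025 and 80% power (5.6).

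**Inputs not in the documents.** The baseline SD (sd0), the baseline-to-day-1 correlation (ρ), and the SD and effect at day 7. These are assumed below and shown over a range. Complete data and a known covariance are also assumed.

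**Step 1: the plan's own figure.** The SE of the unadjusted day-1 difference is 5 × √(2/30) = 1.291. Power for 4 points at two-sided 0.025 is 0.804 by the normal approximation and 0.785 by the exact noncentral t. The stated 80% is reproduced.

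**Step 2: variance of the day-1 contrast** (n = 30 per arm, sd1 = day-1 SD).

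- Separate baseline means: (2/n)(sd0² + sd1² − 2ρ·sd0·sd1).
- Common baseline mean: (2/n)·sd1²(1 − ρ²).
- Difference: (2/n)(sd0 − ρ·sd1)². This is never negative and is zero when sd0 = ρ·sd1.

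Generalised least squares fits at days 0, 1, 7 and at days 0, 1, 7, 30, with equal SDs under compound-symmetry and autoregressive covariances, give the same variances.

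**Step 3: numbers, with sd1 = 5.**

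| sd0 | ρ | SE, separate | SE, common | Variance ratio |
|---|---|---|---|---|
| 5 | 0.3 | 1.53 | 1.23 | 0.65 |
| 5 | 0.5 | 1.29 | 1.12 | 0.75 |
| 5 | 0.7 | 1.00 | 0.92 | 0.85 |
| 2.5 | 0.3 | 1.26 | 1.23 | 0.96 |
| 2.5 | 0.5 | 1.12 | 1.12 | 1.00 |
| 2.5 | 0.7 | 0.96 | 0.92 | 0.93 |

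Example at sd0 = 2.5, ρ = 0.3: separate, (2/30)(6.25 + 25 − 7.5) = 1.583; common, (2/30)(25)(0.91) = 1.517; difference, 2(2.5 − 1.5)²/30 = 0.067.

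**Step 4: when the interaction is worse than ignoring baseline.** The separate-baseline variance exceeds (2/n)sd1² when sd0² > 2ρ·sd0·sd1, that is, when ρ < sd0/(2·sd1). The threshold is 0.5 if sd0 = 5 and 0.25 if sd0 = 2.5.

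**Step 5: joint test over days 1 and 7.** Further assumptions: effects of 4 and 2 points, SD 5 at day 7, equal correlation between all visits, noncentral F with 2 and 58 df, alpha 0.05. Power, separate versus common baseline:

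| ρ | sd0 = 5 | sd0 = 2.5 |
|---|---|---|
| 0.2 | 56% vs 84% | 79% vs 84% |
| 0.3 | 62% vs 85% | 82% vs 85% |
| 0.5 | 78% vs 90% | 90% vs 90% |
| 0.7 | 95% vs 97% | 96% vs 97% |

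**Step 6: if the draw followed the first dose.** Suppose the baseline sample already carried a fraction f of a true −4 effect. With equal SDs, the separate-baseline contrast estimates −4(1 − f) and the common-baseline contrast −4(1 − ρf). At f = 0.25 and ρ = 0.5 these are −3.0 and −3.5, so both are biased towards zero.

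**Step 7: continuous time.** Here the interaction is a difference in slopes. For days 0, 1, 7 under compound symmetry, the centred times are −8/3, −5/3 and 13/3, with sum of squares 258/9 = 28.67. An effect of −4 at day 1 alone gives a slope difference of (−4)(−5/3)/28.67 = +0.23 per day, opposite in sign to the effect.

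**The case against.** The strongest reply is that this is a choice of efficiency within exploratory models. The planned interaction is unbiased under randomisation with a pre-dose baseline, it is a conventional way to study kinetics, and 5.3 labels the monocyte models exploratory. Section 5.4 places the day-7 and day-30 measurements in the secondary or exploratory tier. All of that stands, and it limits the weight of the point.

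Three further objections also stand.

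- **Separate baseline means are inferred.** The plan names the contrast but does not write the model. A constrained model can also be written with treatment-by-post-baseline-visit terms. The point is therefore about the ordinary fit of what is described; if a constraint was intended, one sentence would say so.
- **The size of the loss is unknown.** A reader might infer a large loss of power, such as 56% against 84%. That figure needs ρ = 0.2 together with a baseline SD of 5. The documents give SD 5.0 for day 1 only, and section 4 describes a marked expansion of these monocytes within 24 hours, so equal SDs cannot be presumed. Nor is ρ = 0.5 a general threshold below which the interaction does worse than ignoring baseline; the threshold depends on sd0/sd1.
- **The baseline is not documented as pre-dose.** A reader might take the draw to be pre-treatment and the constraint to be free of any condition. The text says only that the draw precedes TAVR, as does the loading dose. If the dose came first, the constraint would impose an equality that need not hold. Step 6 shows that the separate-baseline contrast would be biased as well, so this does not rescue the plan as written, but it makes the order of draw and dose a necessary part of the fix.

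None of this removes the core: with a pre-dose sample, the common-baseline contrast is never less precise in the calculation above, and it uses data already collected.

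**Conclusion.** The point holds for the categorical-time models, for monocytes and for the secondary markers, on condition that the baseline sample precedes the first study dose. As ordinarily fitted, these models test a difference in change from baseline and can give away precision.

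The day-1 variance reduction ranges from zero upwards. It is 35%, 25% and 15% at ρ = 0.3, 0.5 and 0.7 if the baseline SD is also 5, and 4%, 0% and 7% if it is 2.5. Both SDs and all values of ρ are assumptions, except the day-1 SD for monocytes. No SD or effect size is given for any secondary marker, so it cannot be said that real effects will be missed there.

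The change-score argument does not extend to the continuous-time models, whose interaction is a slope difference. Nor does the point touch the co-primary t-tests, their alpha or the sample size. It is a worthwhile improvement to secondary and exploratory analyses, not a flaw in the trial's main inference.

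**What to change.** 1. In 5.2 and 5.3, state that the baseline sample is drawn before the first study dose. The constraint depends on this, so the order should be confirmed against actual practice.
2. In 5.3, for the categorical-time models of monocytes and secondary markers, keep baseline as an outcome but give both arms one common baseline mean, with an unstructured within-patient covariance. Adjusting for baseline as a covariate is an acceptable alternative.
3. Test the arm differences at the post-baseline visits: days 1 and 7, or days 1, 7 and 30 in the extended model. With baseline kept as an outcome, the within-group kinetics come from the same fit.
4. Say that the continuous-time interaction estimates a difference in slopes, and interpret it separately.

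The cost is a few sentences and a changed model statement. No patients, visits or assays are added, and the number of tested degrees of freedom is unchanged (two, or three with day 30).
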